10.2. Evaluation of Adverse Events

A qualified Sponsor Investigator will evaluate all adverse events as to:

10.2.1. Seriousness

A serious adverse event (SAE) is any AE occurring at any dose that:

- Results in death;
- Is life-threatening (ie, in the opinion of the Sponsor Investigator, the subject is at immediate risk of death from the AE);
- Requires inpatient hospitalization or prolongation of existing hospitalization (hospitalization is defined as an inpatient admission, regardless of length of stay);
- Results in persistent or significant disability/incapacity (a substantial disruption of the subject's ability to conduct normal life functions);
- Is a congenital anomaly/birth defect;
- Constitutes an important medical event.

Important medical events are defined as those occurrences that may not be immediately life threatening or result in death, hospitalization, or disability, but may jeopardize the subject or require medical or surgical intervention to prevent one of the other outcomes listed above. Medical and scientific judgment should be exercised in deciding whether such an AE should be considered serious.

Events not considered to be SAEs are hospitalizations which: were planned before entry into the clinical study; are for elective treatment of a condition unrelated to the studied indication or its treatment; occur on an emergency outpatient basis and do not result in admission (unless fulfilling other criteria above); are part of the normal treatment or monitoring of the studied indication and are not associated with any deterioration in condition.

If an AE is considered serious, both the AE page/screen of the CRF and the SAE Report Form must be completed.

For each SAE, the Sponsor Investigator will provide information on severity, start and stop dates, relationship to IP, action taken regarding IP, and outcome.

10.2.2. Severity / Intensity

For both AEs and SAEs, the Sponsor investigator(s) must assess the severity of the event. The AEs will be evaluated for severity according to the following scale:

Grade 1 = Mild

Grade 2 = Moderate

Grade 3 = Severe

10.2.3. Causality

The Sponsor Investigator must determine the relationship between the administration of IP and the occurrence of an AE/SAE as Not Suspected or Suspected as defined below:

Not suspected: The temporal relationship of the adverse event to IP administration makes **a causal relationship unlikely or remote**, or other medications, therapeutic interventions, or underlying conditions provide a sufficient explanation for the observed event.

Suspected: The temporal relationship of the adverse event to IP administration makes **a causal relationship possible**, and other medications, therapeutic interventions, or underlying conditions do not provide a sufficient explanation for the observed event.

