Apremilast in Combination with Clobetasol Spray for the Treatment of Plaque Psoriasis

INVESTIGATIONAL PRODUCT (IP): Apremilast and Clobetasol 0.05% spray

PROTOCOL NUMBER:

DATE FINAL:

EudraCT NUMBER:

IND NUMBER:

SPONSOR NAME / ADDRESS: [name] / [name]

MEDICAL MONITOR / EMERGENCY CONTACT INFORMATION

Name:	[name]
Title:	Principal Investigator/Sponsor Investigator
Address:	[name]
[contact]
E-mail:	[contact]

PROTOCOL SUMMARY

Study Title - Apremilast in Combination with Clobetasol spray for the treatment of plaque psoriasis of the body with or without scalp involvement

Indication – Apremilast is indicated for the treatment of patients with moderate to severe plaque psoriasis who are candidates for phototherapy or systemic therapy

Objectives

Primary Objective – Assessing the efficacy of combining Clobetasol spray with apremilast for the treatment of plaque psoriasis of the body with or without scalp

Secondary Objectives – Assessing the safety and quality of life in patients treated with Clobetasol spray and apremilast for the treatment of plaque psoriasis of the body with or without scalp

Study Design

Study Population- Adults 18 years and older with plaque psoriasis with at least 10% BSA involving the body with or without scalp lesions

Length of Study – 16 weeks

Study Treatments – Clobetasol is a superpotent topical corticosteroid. Many patients who use this may develop a rebound if stopped suddenly¹. Therefore, in this study the drug will be slowly tapered over 6 weeks. Patients with plaque psoriasis on the body with or without scalp involvement (not solely face/folds/hands/feet) begin apremilast at the approved psoriasis dosage. Patients will also begin clobetasol spray 0.05% to affected plaques bid for 2 weeks, then qday for 2 weeks then qod for 2 weeks then stop clobetasol but continue apremilast for a total of 16 weeks.

Overview of Efficacy Assessments – Patients will have BSA x PGA and PASI 75 scores measured at baseline then at 2, 4, 6, 8, 12 and 16 weeks. We will also record pruritus VAS and TSQM version II at all visits. If scalp involvement, we will also report scalp PGA

Primary Clinical Assessment- Proportion of patients achieving PASI 75 at Week 16 from baseline

Additional Clinical Assessments – Adverse Events (AE), Scalp PGA, Pruritus VAS, TSQM version II. Clinical Benefit, mean percent change from baseline in BSA x PGA at Week 16

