3.2. Study Duration- 16 weeks

4. TABLE OF EVENTS

Visit	Screening	Baseline	Apremilast Treatment					
	1	2	3	4	5	6	7	8
Week	Up to 7 days	0	2	4	6	8	12	16
Informed Consent	x							
Inclusion/Exclusion Criteria	x	x						
Medical and Disease History	x							
Height	x							x
Weight	x							x
Sex	x							
Race	x							
Prior/Concurrent Medications/Therapies	x	x	x	x	x ^a	x	x	x
Safety Assessments								
Pregnancy Test and Contraception Education for Females of Child- bearing Potential (FCBP)	x	x						x
Psoriasis Flare or Rebound Assessment	x	x	x	x	x	x	x	x
Adverse Events	x	x	x	x	x	x	x	x
Clinical Efficacy Assessments								
BSAxPGA	x	x	x	x	x	x	x	x
PASI	x	x	x	x	x	x	x	x
Pruritus VAS	x	x	x	x	x	x	x	x
Scalp PGA	x	x	x	x	x	x	x	x
TSQM version II	x	x	x	x	x	x	x	x
Investigational Product Dosing								
Dispense IP		x	x	x	x	x	x	x
Return IP tablets, Count for Compliance			x	x	x	x	x	x

^a Discontinue clobetasol spray 0.05% at Week 6

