8.2. Prohibited Concomitant Medications and Procedures

The following psoriasis medications cannot be administered for the duration of the study:

- Topical corticosteroids, except for study drug, Clobetasol Spray 0.05%
- Phototherapy
- Oral systemic drugs for psoriasis including: methotrexate, cyclosporine, acitretin
- Biologics treatments for psoriasis: adalimumab, etanercept, infliximab, ustekinumab, secukinumab, ixekizumab, brodalumab

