8.3. Required Concomitant Medications and Procedures

Clobetasol spray 0.05% spray is applied to plaques on body and scalp, but not face and folds, BID for 2 weeks. Then qd for 2 weeks then qod for 2 weeks

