10.3. Action Taken

The Sponsor Investigator will report the action taken with Otezla and Clobetasol spray as a result of an AE or SAE, as applicable (e.g., discontinuation of IP, as appropriate) and report if concomitant and/or additional treatments were given for the event.

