10.7. Expedited Reporting of Adverse Events

For the purpose of regulatory reporting, Celgene Drug Safety will determine the expectedness of events suspected of being related to apremilast based on the Sponsor Investigator's Brochure.

Celgene or its authorized representative shall notify the Sponsor Investigator of the following information:

- Any AE associated with the use of Otezla in this study or in other studies that is both serious and unexpected (ie, SUSAR);
- Any finding from tests in laboratory animals that suggests a significant risk for human subjects including reports of mutagenicity, teratogenicity, or carcinogenicity.

Where required by local legislation, the Sponsor Investigator shall notify his/her IRB/EC promptly of these new serious and unexpected AE(s) or significant risks to subjects.

The Sponsor Investigator must keep copies of all pertinent safety information on file including correspondence with Celgene and the IRB/EC, (see Section 14.2 for record retention information).

Please refer to the Serious Adverse Event Report Form / Completion Guidelines or to the Pregnancy Report Form / Completion Guidelines

Pregnancies and suspected pregnancies (including a positive pregnancy test regardless of age or disease state) of a female subject or the female partner of a male subject occurring while the subject is on study drug, or within 30 days of the subject's last dose of study drug, are considered immediately reportable events. Study drug is to be discontinued immediately and the subject instructed to return any unused portion of the study drug to the Sponsor Investigator(s). The pregnancy, suspected pregnancy, or positive pregnancy test must be reported to Celgene Safety immediately facsimile using the Pregnancy Report form provided by Celgene.

The female should be referred to an obstetrician-gynecologist experienced in reproductive toxicity for further evaluation and counseling.

The Sponsor Investigator(s) will follow the female subject until completion of the pregnancy, and must notify Celgene Safety of the outcome of the pregnancy as a follow-up on the follow up Pregnancy Reporting form.

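### One causality rating against IP gives apremilast-related and clobetasol-related adverse events the same code, although Section 10.7 needs events suspected of being related to apremilast

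*Combined protocol and SAP*

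**What the plan says.** **Causality.** Section 10.2.3 requires one judgement per event, the relationship to IP, with two possible answers. Not suspected applies if the timing makes a causal link unlikely, or if "other medications, therapeutic interventions, or underlying conditions provide a sufficient explanation for the observed event". Suspected applies if the timing makes a link possible and no such alternative explains the event. For serious events, Section 10.2.1 likewise lists one relationship to IP. Neither section asks for a rating per product.

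**What IP means.** The title page is explicit: "INVESTIGATIONAL PRODUCT (IP): Apremilast and Clobetasol 0.05% spray". Section 7 describes both products as study treatments, Section 7.1.3 covers both under investigational-product storage, and Section 8.2 calls the spray study drug: "Topical corticosteroids, except for study drug, Clobetasol Spray 0.05".

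**Where clobetasol is labelled differently.** Under the heading "8.3. Required Concomitant Medications and Procedures", the only content is the spray: "Clobetasol spray 0.05% spray is applied to plaques on body and scalp, but not face and folds". In the Table of Events, the note "Discontinue clobetasol spray 0.05% at Week 6" hangs on the prior and concurrent medication row, and the row for returned IP mentions tablets only.

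**What is recorded or needed by product.** Section 10.3 names both: "The Sponsor Investigator will report the action taken with Otezla and Clobetasol spray as a result of an AE or SAE". Section 10.7 concerns one product: "Celgene Drug Safety will determine the expectedness of events suspected of being related to apremilast".

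**The concern.** Safety of the combination is a secondary objective, and adverse events come first in the list in Section 2.2. The protocol itself associates particular harms with the topical steroid: rebound on sudden stopping (Protocol Summary), and adrenal suppression and skin atrophy with long-term use (Section 1). It also titrates apremilast to limit gastrointestinal symptoms (Section 3). The two products are therefore expected to have different harms, and a reader of the safety data will want to know which product an event was thought to come from.

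The prescribed rating does not record that. It also uses a term that the protocol labels in two ways, and the Not suspected definition turns on what counts as another medication. What is at stake is the meaning of the Suspected code, and whether the apremilast-specific judgement that Section 10.7 presupposes is ever recorded by the assessor who saw the patient.

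**Working it through.** There is no figure in the plan to reproduce and no calculation to run. The check is to apply the Section 10.2.3 definitions to three kinds of event whose timing fits both products, and see which code results.

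**Readings**
- Reading A: IP is both products (title page; supported by Sections 7, 7.1.3, 8.2 and 10.3).
- Reading B: clobetasol is a concomitant medication and so an other medication (suggested by Section 8.3, the Table of Events footnote and the IP-tablets row; Section 10.5 also defines overdose for the tablets only).

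| Event | Reading A | Reading B |
|---|---|---|
| 1. Explained by apremilast only | Suspected | Suspected |
| 2. Explained by clobetasol only | Suspected | Not suspected |
| 3. Either product would be a sufficient explanation | Suspected | Not suspected |

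**Step 1: Reading A taken as correct.** All three rows carry the same code. Section 10.7 needs rows 1 and 3 but not row 2, and the code cannot separate them. The gap therefore exists without any inconsistency in labels.

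**Step 2: Reading B.** Row 2 changes code. Row 3 also becomes Not suspected, although apremilast remains a possible cause. This reading does not supply what Section 10.7 needs either.

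**Step 3: which reading is stronger.** Reading A rests on the only explicit definition. Within Section 10 itself, 10.3 names both products and uses discontinuation of IP as its example. Reading B rests on a heading, a footnote and loose row wording, none of which says that the spray is not IP. The two readings are not equally good, but no sentence in the protocol rules out B for the causality rating.

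**Step 4: where it would bite.** Section 5 defines rebound as an adverse event occurring after treatment is discontinued. The schedule is 6 weeks on both products, then 16 − 6 = 10 weeks on apremilast alone. At Week 6 one product stops and the other continues. A rating against joint IP does not show which of the two was suspected.

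**Step 5: planned statistics affected.** Section 9.1 promises counts for the primary and secondary objectives. Section 9.5 details efficacy only. No section plans a rate or table of treatment-related events.

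**The case against.** The strongest reply is that the title page settles the definition, that other medications naturally means medications other than IP, and that Section 8.3 merely restates the regimen. That largely stands. A reader might infer that the two codings are equally open, so that the recorded result depends on which section the assessor follows. The documents do not support that; inconsistent coding is a risk only. The reply does not reach Step 1, which assumes the title-page definition throughout.

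A second reply is that attribution is not lost. Start and stop dates are kept (Section 10.2.4), action taken is recorded by product (10.3), serious events carry a detailed description (10.6), and the case report and SAE forms are not among the documents and might hold product-level fields. This stands against any claim that events cannot be attributed to a product. The supportable statement is narrower: the protocol does not require a rating per product.

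A third is that reporting does not hang on the rating. Section 10.6 sends serious events during the study, or made known within 30 days of the last dose, to the apremilast supplier regardless of relationship, and also provides for reporting to the clobetasol manufacturer. This stands as well: for those events no report is lost. Section 10.7 does not say that the Section 10.2.3 rating is its only input, so one should not infer that the expectedness review is unworkable.

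Finally, a joint rating does serve an objective framed around the combination. It does so less informatively than two ratings would, at almost the same cost.

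**Conclusion.** The point holds as a cheap improvement to safety recording. Followed exactly, Sections 10.2.1 and 10.2.3 give apremilast-related and clobetasol-related events one code, which does not supply the apremilast-specific judgement in Section 10.7 and is out of step with the per-product record in Section 10.3. The labels in Section 8.3 and the Table of Events add a secondary risk of a Not suspected code for events explained by clobetasol.

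No numerical size should be attached. A reader might be tempted to express the conflict as a shift in the proportion of the 20 patients with a related event. That needs an assumed number of patients with clobetasol-explained events and the weaker reading applied to every one of them; the documents support neither, and Section 9 plans no such proportion. If no clobetasol-related event occurs, nothing changes. The PASI-75 endpoint is unaffected in every case.

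The conclusion assumes that the unseen forms follow the protocol text. If they already carry a causality field per product, only the wording needs correcting.

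**What to change.** 1. In Sections 10.2.3 and 10.2.1, record relationship separately for apremilast and for clobetasol spray.
2. State that neither study product counts as an other medication for this rating. Without this, an event that either product could explain might be coded Not suspected for both. Also state that an event may be suspected for one product, both or neither, each judged in its own right; otherwise, with both products in use, timing alone could mark both.
3. Reconcile the labels in Section 8.3 and the Table of Events with the title-page definition of IP. This concerns labelling only; no dose, schedule or clinical rule is involved.
4. Optional: list adverse events by onset, Weeks 0–6 against after the scheduled clobetasol stop, from the start dates already collected. This is descriptive and does not by itself attribute events to a product: apremilast titration falls in the first period, and rebound after stopping clobetasol would fall in the second, when only apremilast is taken.

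The cost is one extra causality field on the AE and SAE forms and a few lines of text, with no new visit or procedure. Items 1 to 3 are best settled before data collection, because an assessor's judgement not recorded at the time is hard to reconstruct.

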10.2.4. Duration

For both AEs and SAEs, the Sponsor Investigator will provide a record of the start and stop dates of the event.

10.3. Action Taken

The Sponsor Investigator will report the action taken with Otezla and Clobetasol spray as a result of an AE or SAE, as applicable (e.g., discontinuation of IP, as appropriate) and report if concomitant and/or additional treatments were given for the event.

10.4. Outcome

All SAEs that have not resolved upon discontinuation of the subject's participation in the study must be followed until recovered, recovered with sequelae, not recovered (death due to another cause), or death (due to the SAE).

10.5. Overdose

Abuse, withdrawal, sensitivity, or toxicity to an investigational product should be reported as an AE. Overdose, accidental or intentional, whether or not it is associated with an AE should be reported as an AE. Any sequela of an accidental or intentional overdose of an investigational product should be reported as an AE.

If the sequela of an overdose is an SAE, then the sequela must be reported on an SAE report form. The overdose resulting in the SAE should be identified as the cause of the event on the SAE report form but should not be reported as an SAE itself.

In the event of an overdose, the subject should be monitored as appropriate and should receive supportive measures as necessary. There is no known specific antidote for apremilast overdose. Actual treatment should depend on the severity of the clinical situation and the judgment and experience of the treating physician.

Overdose for this protocol, on a per dose basis, is defined as ingestion of any more than the amount prescribed of apremilast tablets in any 24-hour period whether by accident or intentionally.

10.6. Reporting of Serious Adverse Events

Any AE that meets the any criterion for a SAE requires the completion of an SAE Report Form in addition to being recorded on the AE pages of the CRF. The Sponsor Investigator(s) is required to ensure that the data on these forms is accurate and consistent. This applies to all SAEs, regardless of relationship to study drug, that occur during the study, those made known to the Sponsor Investigator(s) within 30 days after a subject's last dose of study drug, and those made known to the Sponsor investigator(s) at any time that are suspected of being related to study drug.

The SAE will be reported to the manufacturer of Clobetasol spray.

The SAE must be reported immediately (i.e., within 24 hours of the Sponsor Investigators' knowledge of the event) to Celgene Safety by facsimile. A written report (prepared by the Sponsor Investigator(s) using an SAE Report Form or a 3500A Medwatch form is to be faxed to Safety (see below for contact information).

Celgene Drug Safety Contact Information:

Celgene Corporation
Global Drug Safety and Risk Management
[name]
[name]
[contact]
E-mail: [contact]

The SAE report should provide a detailed description of the SAE. If a subject has died and an autopsy has been performed, copies of the autopsy report and death certificate are to be sent to Celgene as soon as these become available. Any follow-up data will be detailed in a subsequent SAE Report Form or Medwatch form and sent to Celgene.

The Sponsor Investigator(s) is responsible for informing the Institutional Review Board/Ethics Committee (IRB/IEC) of the SAE and providing them with all relevant initial and follow-up information about the event. The Sponsor Investigator(s) must keep copies of all SAE information, including correspondence with Celgene and the IRB/IEC, on file. All SAEs that have not resolved upon discontinuation of the subject's participation in the study must be followed until either the event resolves completely, stabilizes/resolves with sequelae, or returns to baseline (if a baseline value is available).

10.7. Expedited Reporting of Adverse Events

For the purpose of regulatory reporting, Celgene Drug Safety will determine the expectedness of events suspected of being related to apremilast based on the Sponsor Investigator's Brochure.

Celgene or its authorized representative shall notify the Sponsor Investigator of the following information:

- Any AE associated with the use of Otezla in this study or in other studies that is both serious and unexpected (ie, SUSAR);
- Any finding from tests in laboratory animals that suggests a significant risk for human subjects including reports of mutagenicity, teratogenicity, or carcinogenicity.

Where required by local legislation, the Sponsor Investigator shall notify his/her IRB/EC promptly of these new serious and unexpected AE(s) or significant risks to subjects.

The Sponsor Investigator must keep copies of all pertinent safety information on file including correspondence with Celgene and the IRB/EC, (see Section 14.2 for record retention information).

Please refer to the Serious Adverse Event Report Form / Completion Guidelines or to the Pregnancy Report Form / Completion Guidelines

Pregnancies and suspected pregnancies (including a positive pregnancy test regardless of age or disease state) of a female subject or the female partner of a male subject occurring while the subject is on study drug, or within 30 days of the subject's last dose of study drug, are considered immediately reportable events. Study drug is to be discontinued immediately and the subject instructed to return any unused portion of the study drug to the Sponsor Investigator(s). The pregnancy, suspected pregnancy, or positive pregnancy test must be reported to Celgene Safety immediately facsimile using the Pregnancy Report form provided by Celgene.

The female should be referred to an obstetrician-gynecologist experienced in reproductive toxicity for further evaluation and counseling.

The Sponsor Investigator(s) will follow the female subject until completion of the pregnancy, and must notify Celgene Safety of the outcome of the pregnancy as a follow-up on the follow up Pregnancy Reporting form.

If the outcome of the pregnancy meets the criteria for immediate classification as a SAE (i.e., spontaneous or therapeutic abortion [any congenital anomaly detected in an aborted fetus is to be documented], stillbirth, neonatal death, or congenital anomaly [including that in an aborted fetus]), the Sponsor Investigator(s) should follow the procedures for reporting SAEs (i.e., report the event to Celgene Safety by facsimile within 24 hours of the Sponsor Investigator's knowledge of the event).

In the case of a live "normal" birth, Celgene Safety should be advised by facsimile within 24 hours of the Sponsor Investigator's knowledge of the event.

All neonatal deaths that occur within 30 days of birth should be reported, without regard to causality, as SAEs. In addition, any infant death after 30 days that the Sponsor Investigator(s) suspects is related to the in utero exposure to the study drug should also be reported to Celgene Safety by facsimile within 24 hours of the Sponsor Investigators' knowledge of the event. If the female is found not to be pregnant, any determination regarding the subject's continued participation in the study will be determined by the Sponsor Investigator.

If a female partner of a male subject taking IP becomes pregnant, the male subject taking IP should notify the Sponsor Investigator, and the pregnant female partner should be advised to call their healthcare provider immediately.

